6.3.2 Stratification

No stratification based on age, sex, or other characteristics will be used in this study.

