9.6 Statistical Methods

9.6.1 Statistical Methods for Immunogenicity Analyses

This section describes the statistical methods that address the primary and secondary immunogenicity objectives. Methods related to exploratory objectives will be described in the sSAP.

Immunogenicity analyses will be conducted for each serotype separately.

Primary Endpoint/Hypothesis (H1)

The primary objective to compare the serotype-specific OPA GMTs at 30 days postvaccination across the 3 different lots of V116 for all serotypes included in V116 will be assessed via the primary hypothesis.

Each possible pairwise comparison of lots will be made (Lot 1 to Lot 2, Lot 1 to Lot 3, and Lot 2 to Lot 3). Each possible pairwise comparison of lots will consist of two 1-sided tests at the type 1 error = 0.025 level. Rejecting the null hypothesis of nonequivalence for any test is equivalent to requiring the bounds of the 95% CI on the pairwise lot-to-lot comparison of the V116 GMT ratios to be between 0.5 and 2.0.

For each serotype in V116 and for each pairwise comparison, OPA GMTs between participants administered different lots of V116 at 30 days postvaccination will be compared via the following equivalence hypotheses:

H₀: GMT_x/GMT_y \leq 0.5 or GMT_x/GMT_y \geq 2.0 versus H₁: 0.5 < GMT_X/GMT_y <2.0

where GMT_x is serotype-specific OPA GMT for one of the V116 lots and GMT_y is serotype-specific OPA GMT for another V116 lot. A ratio between 0.5 and 2.0 corresponds to ensuring that there's no more than a 2.0-fold difference between OPA GMTs across any of the V116 lots (Lot 1 vs Lot 2, Lot 1 vs Lot 3, and Lot 2 vs Lot 3). Rejecting the null hypothesis (H₀) at the two 1-sided type 1 error = 0.025 level corresponds to the bounds of the 95% CI on the GMT ratio between each V116 lot (Lot 1/Lot 2, Lot 1/Lot 3, and Lot 2/Lot 3) being between 0.5 and 2.0 and would lead to the conclusion that the OPA responses across the V116 lots are equivalent.

Estimation of the GMT ratios, 95% CIs, and the hypothesis test (ie, 1-sided p-value) will be conducted using a cLDA method proposed by Liang and Zeger [Liang, K-Y and Zeger, S. L. 2000] utilizing data from the participants randomized to the 3 V116 lots. In this model, the response vector consists of the log-transformed antibody titers at baseline and 30 days postvaccination. The repeated-measures model will include terms for vaccination group (V116 Lot 1, V116 Lot 2, and V116 Lot 3), time, and the interaction of time-by-vaccination

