OPA GMTs ^c and IgG GMCs ^c at 30 days postvaccination for all serotypes included in V116	Р	cLDA ^b (estimate, 95% CI)	РР	Model-based	
GMFRs and proportions of participants with a \geq 4-fold rise from baseline to 30 days postvaccination for both OPA and IgG responses for all serotypes included in V116	р	Descriptive Statistics (estimate, 95% CI)	РР	Missing data will not be imputed	
OPA GMTs at 30 days postvaccination for the cross- reactive serotypes	Р	Descriptive Statistics (estimate, 95% CI)	РР	Missing data will not be imputed	

Table 5Analysis Strategy for Immunogenicity Variables

CI = confidence interval; cLDA = constrained longitudinal data analysis; FAS = Full Analysis Set;

GMC = Geometric Mean Concentration; GMFR = geometric mean fold rise; GMT = Geometric Mean Titer; IgG = Immunoglobulin G; OPA= opsonophagocytic killing activity; PP = Per-Protocol.

^a P = Primary approach; S = Supportive approach.

cLDA model with terms for vaccination group, time, and the interaction of time-by-vaccination.

^c Include the following endpoints: serotype-specific OPA GMTs at 30 days postvaccination in combined lots of V116 compared with PPSV23; serotype-specific IgG GMCs at 30 days postvaccination compared across the 3 different lots of V116 and combined lots of V116 compared with PPSV23.

Baseline is the day of vaccination (Day 1); 30 days postvaccination is the day of the Visit 3 blood draw (Day 30).

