9.6.3 Demographic and Baseline Characteristics

The comparability of the vaccination groups for each relevant demographic and baseline characteristic will be assessed using summary tables. No statistical hypothesis tests will be performed on these characteristics. The number and percentage of participants randomized and discontinued from the study and discontinuation reasons will be displayed. Demographic variables (age, race, ethnicity, sex, and gender), baseline characteristics, and prior and concomitant vaccinations and medications will be summarized by intervention group either by descriptive statistics or categorical tables.

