9.9 Sample Size and Power Calculations

9.9.1 Sample Size and Power for Immunogenicity Analyses

This study will randomize approximately 510 participants to receive each of 3 manufactured lots of V116 (Lot 1, Lot 2, and Lot 3) and 510 participants to receive PPSV23.

Primary Immunogenicity Endpoint/Hypothesis (H1)

For the primary hypothesis, this study has >90% power to demonstrate equivalent immunogenicity across the 3 V116 lots as assessed by the OPA GMTs at 30 days postvaccination for all serotypes contained in V116 at an overall type 1 error = 0.05 (2-sided). The power and sample size are based on the following assumptions:

 90% evaluability rate (approximately 459 evaluable participants in each of 3 manufactured lots of V116)

V116-004-01 FINAL PROTOCOL

63

- The underlying serotype-specific OPA GMT ratios are 1.0 for all serotypes
- The variabilities for OPA titers in the V116 vaccination groups are the same as those observed in V116-001 Phase 2 for all serotypes. That is, the standard deviations of the natural log titers range from 1.06 to 1.95

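### The cLDA uses baseline titer as its only prognostic variable; prespecifying age and sex as well would be a small, nearly free gain in precision, mainly for the secondary GMT and GMC ratios.

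*Combined protocol and SAP*

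**What the plan says.** Randomization is 1:1:1:1 with no stratification (Section 6.3.2): "No stratification based on age, sex, or other characteristics will be used in this study".

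The primary model in Section 9.6.1 takes baseline and Day 30 log titers as a two-part response, holds the baseline mean equal across lots, and uses an unstructured covariance. Its terms are given as: "The repeated-measures model will include terms for vaccination group (V116 Lot 1, V116 Lot 2, and V116 Lot 3), time, and the interaction" of time with group. Table 5 footnote b repeats this for every endpoint analyzed by cLDA: "cLDA model with terms for vaccination group, time, and the interaction of time-by-vaccination". Section 9.6.1 carries a similar model over to the secondary IgG lot ratios and to the combined V116 versus PPSV23 ratios for OPA and IgG.

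Age and sex appear elsewhere. Section 9.6.3 lists "Demographic variables (age, race, ethnicity, sex, and gender), baseline characteristics" among the items to be summarized by group, and Section 9.10 names sex, but not age, as a subgroup. The only supportive analysis of the primary endpoint is the same cLDA in the FAS (Section 9.5.1, Table 5). No covariate-adjusted analysis is planned.

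**The concern.** Day 30 titer variation that age and sex explain beyond baseline titer stays in the error term, and chance imbalance in them between arms is not adjusted for. In a linear model on the log scale, adding baseline covariates without a group interaction leaves the GMT or GMC ratio with the same meaning, and it narrows the interval to the extent that they are prognostic. The plan already takes this view of efficiency: it puts baseline titer in the response vector and keeps participants with one missing sample for that reason.

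What is at stake is interval width. The secondary ratios have no hypothesis or success criterion in Section 3, so precision is all that adjustment can improve there. For the primary objective, narrower intervals would add a little margin if true lot ratios are not exactly 1.0.

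**Working it through.** **Inputs.** From Section 9.6.1: "Each possible pairwise comparison of lots will consist of two 1-sided tests at the type 1 error = 0.025 level", which the plan equates with "requiring the bounds of the 95% CI on the pairwise lot-to-lot comparison of the V116 GMT ratios to be between 0.5 and 2.0". The margin on the log scale is therefore ±ln 2 = ±0.693. From Section 9.9.1: 510 randomized per lot and 90% evaluable, so 510 × 0.9 = 459; SDs of natural log OPA titer from 1.06 to 1.95; and "The underlying serotype-specific OPA GMT ratios are 1.0 for all serotypes". From Section 9.8: all 3 pairs must succeed for all 21 serotypes, which is 63 comparisons.

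**Step 1: the plan's own figure.** Section 9.9.1 states: "For the primary hypothesis, this study has >90% power to demonstrate equivalent immunogenicity across the 3 V116 lots". At the largest SD:

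- SE of a log lot ratio = 1.95 × √(2/459) = 0.1287
- power for one pair = 2Φ(0.693/0.1287 − 1.96) − 1 = 2Φ(3.425) − 1 = 0.99939
- all 63 comparisons, treated as independent = 0.99939^63 = 96.2%

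Simulating the correlated pairs gives 96.3%. With the 21 SDs spread evenly from 1.06 to 1.95, the product is 99.5%. The stated figure reproduces.

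**Step 2: effect of adjustment.** Let R² be the share of residual Day 30 log-titer variance explained by age and sex. The documents give no value, so 1%, 5% and 10% are assumed. The SE is multiplied by √(1 − R²), which is 0.995, 0.975 and 0.949. The 95% CI factor for a lot ratio is exp(1.96 × 1.95 × √(2/459) × √(1 − R²)), and the equivalent evaluable number per lot is 459/(1 − R²).

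| R² | Fall in SE | Lot-ratio CI factor | Equivalent n per lot | Power, all SDs 1.95 |
|---|---|---|---|---|
| 0 | none | 1.287 | 459 | 96.2% |
| 1% | 0.5% | 1.285 | 464 | 96.6% |
| 5% | 2.5% | 1.279 | 483 | 97.7% |
| 10% | 5.1% | 1.270 | 510 | 98.7% |

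**Step 3: combined V116 versus PPSV23.** With 3 × 459 = 1377 against 459, the factor is exp(1.96 × 1.95 × √(1/1377 + 1/459) × √(1 − R²)). It goes from 1.229 to 1.227, 1.222 or 1.216. This assumes that the largest V116 OPA SD also applies to PPSV23, for which the documents give none. They give no IgG SD either, so no IgG figure can be calculated.

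**Step 4: allowing for baseline titer.** Steps 2 and 3 use the full SD and ignore what baseline titer already explains. If its correlation with Day 30 titer were 0.5 (an assumption), the residual SD would be 1.95 × √(1 − 0.25) = 1.689. The lot-ratio factor would start at 1.244 and move to 1.237 at R² = 5%. The absolute gain is then smaller than in the table.

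**Step 5: cost if age and sex are not prognostic.** Simulated lot contrasts with 459 per lot and baseline correlations of 0, 0.3 and 0.5, using ANCOVA as a stand-in for the cLDA, gave ratios of adjusted to unadjusted SE of about 1.00 at R² = 0, about 0.98 at 5%, and 0.94 to 0.96 at 10%. Adding the terms costs essentially nothing when they do not help.

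**The case against.** The strongest reply is that nothing is wrong as written. Because randomization used no stratification factors, the model omits none, and its intervals already allow for chance imbalance. Power is at least 96% on the plan's inputs, and 99.5% with the SDs spread evenly, so at most half a percentage point remains to gain there. The gain itself is assumed, age is restricted to 18 to 49 years, and a factor of 1.287 is far inside a margin of 2.0. All of that stands.

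The power argument has limits. It depends on every true ratio being 1.0: at a true ratio of 1.3 and SD 1.95, single-pair power is 91.7% without adjustment, 93.0% at R² = 5% and 94.2% at 10%. It also does not bear on the estimation-only secondary ratios, although no decision rests on those.

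A reader might infer that unstratified randomization without covariates biases the lot ratios or inflates the type I error. The documents do not support that: randomization protects the unadjusted contrast. A reader might also infer that the model-based handling of missing titers is deficient without age and sex. Nothing in the documents suggests that missingness depends on either, and the 90% evaluability rate may include per-protocol exclusions as well as missing samples.

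**Conclusion.** This is a missed efficiency of minor importance, not an error. The planned cLDA is valid and its power claim holds. No bias, type I error problem or missing-data defect is claimed.

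The improvement amounts to standard errors lower by about 0.5% to 5%, on the assumption that age and sex explain 1% to 10% of the residual Day 30 log-titer variance. The true share could lie at or below the bottom of that range. No equivalence conclusion is shown to change. The case for acting is that the variables are already planned for collection, the ratio keeps its meaning, and the cost is close to zero. It is clearest for the secondary IgG lot ratios and the V116 versus PPSV23 ratios.

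**What to change.** Before unblinding:

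1. **Secondary ratios.** In Section 9.6.1 and Table 5 footnote b, add age (continuous) and sex, each with a time interaction, to the cLDA for the IgG lot ratios and for the combined V116 versus PPSV23 OPA and IgG ratios. The time interactions let the covariate effects differ between baseline and Day 30.
2. **Primary OPA lot comparison.** Choose one of two routes. Either add the same terms by protocol amendment, naming one model as decisive so that there is no ambiguity if two models disagree near the margin; or leave the primary model as it is and prespecify the adjusted model as a supportive analysis.

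The cost is two covariates and their time interactions in existing code, plus the wording. No new data are needed, and the lost degrees of freedom are negligible with 2 × 459 = 918 evaluable per lot pair. The opening of Section 9 requires an amendment if the primary method changes after the study has begun. It allows changes to nonconfirmatory analyses to be documented in the sSAP, so the supportive route is the lighter one.

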9.6.2 Statistical Methods for Safety Analyses

Safety and tolerability will be assessed by clinical review of all relevant parameters, including AEs and postvaccination temperature measurements.

Consistency of the safety profile across lots will be assessed via point estimates and 95% CIs (for select safety endpoints) for each lot of the V116 separately. Details will be provided in the sSAP. The evaluation of safety will be performed for V116 overall (combining the Lot 1, Lot 2, and Lot 3) versus the PPSV23 group as detailed below (Table 6).

9.6.2.1 Overall Safety Assessment

The overall safety evaluation will include a summary (ie, number and percentage) by intervention group (V116 overall and PPSV23 group) of participants with any AEs, any unsolicited AEs, any vaccine-related AEs, any SAEs, any vaccine-related SAEs, and any AEs resulting in death after vaccination. Point estimates and 95% CIs for the between-treatment differences (combined lots of V116 compared with PPSV23) in the percentages of participants with the event will be provided for these events.

The number and percentage of participants with specific AEs will also be provided. Point estimates and 95% CIs for the differences between intervention groups in the percentages of participants with specific AEs will be provided for solicited AEs and AEs that occur in $\geq 1\%$ of participants in the combined lots of V116 group or PPSV23 group. Events reported less frequently than in 1% of participants would obscure the assessment of the overall safety profile and add little to the interpretation of potentially meaningful differences.

The number and percentage of participants with maximum temperature measurements meeting the Brighton Collaboration cut points [Marcy, S. M., et al 2004] will be provided along with point estimates and 95% CIs of between-group differences to evaluate elevated temperatures.

CIs for between-group differences will be provided using the M&N method [Miettinen, O. and Nurminen, M. 1985]. CIs that are not adjusted for multiplicity should only be regarded as helpful descriptive measures for the review of the safety profile and not as a formal method for assessing statistical significance of between-group differences. Rainfall plots with point estimates and 95% CIs will be displayed for AEs that occur in \geq 5% of participants in the combined lots of V116 group or PPSV23 group.

The analysis strategy for safety endpoints is summarized in Table 6.

Analysis Part	Safety Endpoint	Descriptive Statistics	95% Between- group CI	Graphical Display
Overall Safety	Solicited injection-site AE (Day 1 through Day 5 postvaccination) ^a	X	Х	
Assessment	Solicited systemic AE (Day 1 through Day 5 postvaccination) ^a	Х	Х	
	Any AE ^b	Х	Х	
	Any unsolicited AE ^b	Х	Х	
	Any vaccine-related AE ^b	Х	Х	
	Any SAE ^b	Х	Х	
	Any vaccine-related SAE ^b	Х	Х	
	Death ^b	Х	Х	
	Specific AEs by SOC and PT ^c	Х	Х	Х
	Maximum temperatures (Day 1 through Day 5 postvaccination) ^d	X	Х	

 Table 6
 Analysis Strategy for Safety Parameters

AE=adverse event; CI=Confidence Interval; PT=Preferred term; SAE=serious adverse event; SOC=System Organ Class.

^a Solicited injection-site AEs include redness/erythema, swelling, and tenderness/pain; solicited systemic AEs include muscle aches all over body/myalgia, headache, and tiredness/fatigue.

^b These endpoints are broad AE categories. For example, descriptive statistics for the safety endpoint of "Any AE" will provide the number and percentage of participants with at least 1 AE.

^c Descriptive Statistics, 95% Between-group CI, and Graphical Display will be provided for specific AEs with incidence >0%, \geq 1%, and \geq 5% of participants, respectively, in the combined V116 group or the PPSV23group. ^d Maximum temperature measurements are categorized by Brighton Collaboration cut points.

9.6.3 Demographic and Baseline Characteristics

The comparability of the vaccination groups for each relevant demographic and baseline characteristic will be assessed using summary tables. No statistical hypothesis tests will be performed on these characteristics. The number and percentage of participants randomized and discontinued from the study and discontinuation reasons will be displayed. Demographic variables (age, race, ethnicity, sex, and gender), baseline characteristics, and prior and concomitant vaccinations and medications will be summarized by intervention group either by descriptive statistics or categorical tables.

9.7 Interim Analyses

A periodic review of safety and tolerability data across the V116 Phase 3 adult program will be conducted by an independent, unblinded, external DMC. A description of the structure and function of the DMC, along with the timing and content of the safety review, will be outlined in the DMC charter. Information regarding the composition of the DMC is provided

in Appendix 1. In addition, unblinded immunogenicity data will be made available to the DMC upon request to enable a benefit-risk assessment.

The DMC will serve as the primary reviewer of the results of the ongoing safety reviews and will make recommendations for continuation of the study (with or without protocol modifications) or the discontinuation of the study to an executive oversight committee of the Sponsor (see Appendix 1 for details on the Committees Structure for this study). If the DMC recommends modifications to the design of the protocol or discontinuation of the study, this oversight committee of the Sponsor (and potentially other limited Sponsor personnel) may be unblinded to results at the intervention level to act on these recommendations. The extent to which individuals are unblinded with respect to ongoing safety reviews will be documented by the external unblinded statistician. Additional logistical details will be provided in the DMC charter.

Study enrollment may be ongoing at the time of external DMC review. Blinding to intervention assignment will be maintained at all investigational sites. Participant-level unblinding will be restricted to an external unblinded statistician performing ongoing safety reviews. Intervention-level ongoing safety reviews will be provided by the external unblinded statistician to the DMC. Prior to final study unblinding, the external unblinded statistician will not be involved in any discussions regarding modifications to the protocol, statistical methods, identification of protocol deviations, or data validation efforts after the safety reviews.

9.8 Multiplicity

The study will be considered to have met the primary objective if success is achieved for all 3 pairwise comparisons for V116 lots for all serotypes contained in V116. Since comparisons are made individually for each serotype and for each pairwise comparison, this approach controls the overall type 1 error rate at 0.05 (2-sided), and no multiplicity adjustment is required.

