9.4.1 Immunogenicity Endpoints

Immune responses will be measured for all 21 serotypes contained in V116 (3, 6A, 7F, 8, 9N, 10A, 11A, 12F, 15A, 15C, 16F, 17F, 19A, 20, 22F, 23A, 23B, 24F, 31, 33F, and 35B), and 2 cross-reactive serotypes (6C and 15B).

The primary immunogenicity endpoint is the serotype-specific OPA GMTs at 30 days postvaccination for all serotypes included in V116.

The secondary immunogenicity endpoints for all serotypes contained in V116 include the following:

- Serotype-specific OPA GMTs at 30 days postvaccination in combined lots of V116 compared with PPSV23
- Serotype-specific IgG GMCs at 30 days postvaccination compared across the 3 different lots of V116 and combined lots of V116 compared with PPSV23
- Serotype-specific GMFRs and proportions of participants with a ≥4-fold rise from baseline to 30 days postvaccination for both OPA and IgG responses separately for 3 different lots of V116

The secondary immunogenicity endpoints for cross-reactive immune responses to serotypes within a serogroup include the following:

 Serotype-specific OPA GMTs at 30 days postvaccination separately for 3 different lots of V116

The exploratory immunogenicity endpoints include the summaries of the cross-reactive immune responses to serotypes within a serogroup using serotype-specific OPA and IgG responses at 30 days postvaccination.

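### Does the overall type 1 error of 0.05 (2-sided) stated for the lot-consistency test need correcting to 0.025?

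*Combined protocol and SAP*

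**What the plan says.** Section 9.6.1 (Statistical Methods for Immunogenicity Analyses) sets the null hypothesis for each lot pair and serotype as a GMT ratio of 0.5 or less, or of 2.0 or more. It continues: "Each possible pairwise comparison of lots will consist of two 1-sided tests at the type 1 error = 0.025 level". It equates rejection with requiring "the bounds of the 95% CI on the pairwise lot-to-lot comparison of the V116 GMT ratios to be between 0.5 and 2.0". The lot pairs are "Lot 1 to Lot 2, Lot 1 to Lot 3, and Lot 2 to Lot 3", and Section 9.4.1 lists 21 vaccine serotypes, so there are 3 × 21 = 63 comparisons.

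Section 9.8 (Multiplicity) first gives the success rule: the primary objective is met if "success is achieved for all 3 pairwise comparisons for V116 lots for all serotypes contained in V116". The next sentence gives the reason, "Since comparisons are made individually for each serotype and for each pairwise comparison", and then the conclusion, "this approach controls the overall type 1 error rate at 0.05 (2-sided), and no multiplicity adjustment is required". The summary in Section 9.1 repeats this text, and the power statements in Sections 9.1 and 9.9.1 carry the same 0.05 (2-sided) label.

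**The concern.** Two things look wrong. First, a true ratio cannot sit at 0.5 and at 2.0 at once, so the two 0.025 error rates of one equivalence comparison do not add up to 0.05. On the plan's own definition the error is at most 0.025, which makes the stated figure twice the true maximum. Second, testing comparisons one by one is what creates a multiplicity problem; it does not solve one. Taken alone, the stated reason would equally excuse an unadjusted claim for a single serotype or lot pair.

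This is the study's only formal hypothesis, and Section 4.2 says that the study supports licensure. If the stated level were wrong in the harmful direction, or if the reason opened the way to partial claims, the confirmatory conclusion would be at stake.

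**Working it through.** **Inputs.** Margin 0.5 to 2.0, which is ±ln 2 = ±0.693 on the log scale, and 1-sided level 0.025 (Section 9.6.1). 459 evaluable participants per lot (90% of 510), standard deviations of the natural log titers from 1.06 to 1.95, and true ratios of 1.0 for power (Section 9.9.1). 63 comparisons, all of which must pass (Section 9.8). The check uses a two-sample normal approximation in place of the longitudinal model; this does not affect the nominal level.

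**Where 0.05 comes from.** 2 × 0.025 = 0.05, the complement of a 95% interval. It reproduces as a label for the interval, not as the size of the equivalence test.

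**One comparison at the margin.** SE = SD × √(2/459), which is 0.0700 at SD 1.06 and 0.1287 at SD 1.95. At a true ratio of 2.0, the chance of wrongly declaring equivalence is

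Φ(−1.96) − Φ(−2 ln 2/SE + 1.96).

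Even at SD 1.95 the second term is Φ(−10.77 + 1.96) = Φ(−8.81), effectively zero. The result is 0.0250 at both SDs. Reaching 0.05 would need 1-sided tests at 0.05 (90% intervals), which the plan does not use.

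**All 63 comparisons.** If the overall claim is false, at least one of the 63 nulls is true. Declaring success requires rejecting that one, which has probability at most 0.025. Requiring the others as well can only lower it. This is an intersection-union test, and it needs no adjustment.

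Simulation of three lot means (2,000,000 replicates, one serotype) agrees:

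| True log means of the three lots | SD 1.06 | SD 1.95 |
|---|---|---|
| 0, ln 2/2, ln 2 | 0.0251 | 0.0242 |
| 0, 0, ln 2 | 0.0046 | 0.0047 |

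The 0.0251 is 0.025 within simulation error: √(0.025 × 0.975/2,000,000) = 0.0001. With the other 20 serotypes at ratio 1.0 and taken as independent, the full rule gives 0.0235 to 0.0250 over the SD range.

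**The stated reason.** Under a different rule, in which any one independent test at 0.025 sufficed, the error would be 1 − 0.975^21 = 0.412 for 21 tests and 1 − 0.975^63 = 0.797 for 63. Individual testing alone therefore gives no control. The plan has no such rule.

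**Power at the level actually used.** At ratio 1.0 and SD 1.95, one comparison has power 2Φ(0.693/0.1287 − 1.96) − 1 = 0.99939. If all 21 serotypes had SD 1.95:

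- the Bonferroni lower bound is 1 − 63 × 0.000615 = 0.961;
- the independent product is 0.99939^63 = 0.962;
- simulating the three correlated pairs gives 0.99825 per serotype, and 0.99825^21 = 0.964.

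At SD 1.06 power is essentially 1. The claim of more than 90% therefore holds at 1-sided 0.025.

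**The case for a change.** The best argument for a change is that a multiplicity section exists to state the confirmatory error rate and why it is controlled. Here the level is not the size of the test in Section 9.6.1, and the reason is not the one that works. A reader of Section 9.8 alone could not tell whether the intended level is 0.025 or 0.05. If some of the 63 comparisons failed, someone might use the sentence to defend a claim on the rest. The repair is only a few words.

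Part of this stands. The clause about individual comparisons is misworded, and tying the absence of adjustment to the all-must-pass rule would read better. The rest does not carry. The interval and the 1-sided level are fixed in Section 9.6.1 and in the summary in Section 9.1, and the 95% interval criterion also appears with the objectives in Section 3, so an analyst cannot run the wrong test. The success rule immediately before the loose clause rules out a primary claim on part of the 63. The wording about control at 0.05 can naturally be read as covering that rule, and it is true as an upper bound.

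**Conclusion.** No change to the plan is called for. The strict maximum error is 0.025 against a stated 0.05, so the plan overstates its false-positive risk and hides none. The reason in Section 9.8 is a slip of wording attached to a correct conclusion. Correcting the label and the reason would leave the decision rule, margin, intervals, sample size and power claim (about 96% in the least favourable case examined) as they are.

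This rests on the 95% interval criterion of Section 9.6.1 and the all-63 rule of Section 9.8 being applied as written. The 0.025 bound does not depend on the correlation between serotypes or on the standard deviations. The power figures rest on the assumptions of Section 9.9.1 and the normal approximation. If the text is opened for other reasons, the authors may wish to name the all-must-pass rule as the source of control and put 1-sided 0.025 beside the label; that is optional.
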